### Duration of Each Local Reaction

The duration of each local reaction will be calculated in days as (resolution date of reaction - start date of reaction +1). Resolution of the event is the last day in which the event is recorded in the e-diary or the date the event ends if it is unresolved during the subject diary-recording period (end date collected on the CRF), unless chronicity is established. If there is no known end date, the duration will be considered unknown and set to missing. Subjects with no reported reaction have no duration.

### Onset of Local Reaction

The onset day of each local reaction and any local reaction will be derived.

For the onset day of each local reaction, if subjects report severity change of the local reaction, the first day of initial reporting of that specific local reaction will be counted.

For the onset day of any local reaction, the first day of reporting any severity of any local reaction will be counted.

In summary, the following variables will be derived for local reaction:

1. Presence or absence of each local reaction on each day (Days 1-14) after vaccination.
2. Presence or absence of each local reaction on “any Day 1-14” after vaccination.
3. Maximum severity of each local reaction on “any Day 1-14” after vaccination.
4. Presence or absence of any local reaction on “any Day 1-14” after vaccination.
5. Duration of each local reaction after vaccination.
6. Onset day of each local reaction after vaccination.
7. Onset day of any local reaction after vaccination.

#### **3.6.2.2. Systemic Events**

Systemic events reported via e-diary are: fever, nausea/vomiting, diarrhea, headache, fatigue, muscle pain, and joint pain. The highest temperature for each day for 14 days after vaccination to be recorded in the e-diary. The protocol defines fever as an oral temperature  $\geq 100.4^{\circ}\text{F}$  ( $38.0^{\circ}\text{C}$ ). For ongoing fever on Day 14, the stop date will be recorded in the CRF. Additionally, the subject to document the presence or absence of remaining systemic events in the e-diary as ‘Mild’, ‘Moderate’, ‘Severe’ or ‘None’. Subjects to be asked to assess severity of each event according to the [Table 6](#) below. Only an investigator is able to classify a subject’s systemic event as Grade 4, after physical examination of the subject or documentation from another medically qualified source (e.g., emergency room or hospital record), or telephone contact with the subject. If a subject experiences a Grade 4 systemic event, it will be captured under the unplanned visit CRF page. A severe systemic event entry in the e-diary that later is assessed as Grade 4 will be treated as Grade 4 for analyses.

Any temperature recorded as  $<95.0^{\circ}\text{F}$  ( $35.0^{\circ}\text{C}$ ) or  $>107.6^{\circ}\text{F}$  ( $42.0^{\circ}\text{C}$ ) will be treated as data entry errors and excluded from the analyses. For reporting purposes, fever will be analyzed using the following temperature ranges:

- $100.4^{\circ}\text{F}$  to  $101.1^{\circ}\text{F}$  ( $38.0^{\circ}\text{C}$  to  $38.4^{\circ}\text{C}$ )

- 101.2°F to 102.0°F (38.5°C to 38.9°C)
- 102.1°F to 104.0°F (39.0°C to 40.0°C)
- >104.0°F (>40.0°C)

**Table 6. Systemic Events Grading Scale**

	Mild (Grade 1)	Moderate (Grade 2)	Severe (Grade 3)a	Grade 4b
Nausea/Vomiting	No interference with activity or 1-2 times in 24 hours	Some interference with activity or >2 times in 24 hours	Prevents daily activity; requires IV hydration	Emergency room visit or hospitalization for hypotensive shock
Diarrhea	2-3 loose stools in 24 hours	4-5 loose stools in 24 hours	≥6 loose stools in 24 hours	Emergency room visit or hospitalization
Headache	No interference with activity	Repeated use of non-narcotic pain reliever >24 hours or some interference with activity	Significant; any use of narcotic pain reliever or prevents daily activity c	Emergency room visit or hospitalization
Fatigue/ Tiredness	No interference with activity	Some interference with activity	Significant; prevents daily activity c	Emergency room visit or hospitalization
Muscle pain	No interference with activity	Some interference with activity	Significant; prevents daily activity c	Emergency room visit or hospitalization
Joint pain	No interference with activity	Some interference with activity	Significant; prevents daily activity c	Emergency room visit or hospitalization

Abbreviations: IV = intravenous.

- Subjects experiencing ≥ Grade 3 systemic events are to be seen by the study site.
- Grade 4 assessment should be made by the investigator; a Grade 4 event will not be collected in the e-diary but will be recorded as an AE on the CRF.
- Prevents daily routine activity, i.e., results in missed days of work or school or is otherwise incapacitating, or includes use of narcotics for analgesia.

The presence or absence of each systemic event on a given day is defined as follows:

= missing if value is missing on a given day;

= ‘Yes’, if the subject reports a temperature ≥38.0°C for fever **or** ‘Mild’, ‘Moderate’ or ‘Severe’ or ‘Grade 4’ for the remaining events on a given day;

= ‘No’ if the subject reports a temperature <38.0°C for fever **or** ‘None’ for the remaining events on a given day.

For each systemic event, the following variables will be derived:

1. Presence or absence of each systemic event on each day (up to Day 14) after vaccination.
2. Presence or absence of each systemic event on “any Day 1-14” after vaccination.
3. Maximum severity of each systemic event on “any Day 1-14” after vaccination.
4. Presence or absence of any systemic event on “any Day 1-14” after vaccination.
5. Duration of each systemic event after vaccination.
6. Onset day of each systemic event after vaccination.
7. Onset day of any systemic event after vaccination.

The derivation of these variables is similar to the derivation of the variables for local reactions ([Section 3.6.2.1](#)). Any systemic event includes fever, nausea/vomiting, diarrhea, headache, fatigue/tiredness, muscle pain or joint pain.

### **3.6.2.3. Use of Antipyretic/Pain Medication**

The use and type of antipyretic and/or pain medication will be recorded in the e-diary for 14 days (Days 1-14) after vaccination.

The following variables will be derived similar to the derived variables for local reaction:

1. Use of antipyretic/pain medication on each day (Days 1-14) after vaccination.
2. Use of antipyretic/pain medication on “any Day 1-14” after vaccination.
3. Duration of use of antipyretic/pain medication after vaccination.
4. Onset day of antipyretic use after vaccination.

### **3.6.3. Laboratory Data**

Laboratory data will be collected from the sentinel cohort subjects at screening, at rescreening if applicable, and at Visit 2 (1-week follow-up visit). The parameters of interest at each visit are listed below in [Table 7](#).

**Table 7. Laboratory Tests**

Hematology	Chemistry
Hemoglobin	BUN and Creatinine
Hematocrit	AST, ALT
RBC count	Total bilirubin
Platelet count	Alkaline phosphatase
WBC count	
Total neutrophils (Abs)	
Eosinophils (Abs)	
Monocytes (Abs)	
Basophils (Abs)	
Lymphocytes (Abs)	

Abbreviations: Abs = absolute; ALT = alanine aminotransferase; AST = aspartate aminotransferase; BUN = blood urea nitrogen; RBC = red blood cell; WBC = while blood cell.

The FDA toxicity grading scale in Table 8 below for healthy adult and adolescent volunteers enrolled in the preventive vaccine clinical trials will be adapted for use in grading laboratory test abnormalities.

**Table 8. Hematology and Blood Chemistry Toxicity Grading Scale**

	Mild (Grade 1)	Moderate (Grade 2)	Severe (Grade 3)	Grade 4
Male hemoglobin (Hb)	12.5-13.5 g/dL (125-135 g/L)	10.5-12.4 g/dL (105-124 g/L)	8.5-10.4 g/dL (85-104g/L)	<8.5 g/dL (<85 g/L)
Female hemoglobin (Hb)	11.0-12.0 g/dL (110-120 g/L)	9.5-10.9 g/dL (95-109g/L)	8.0-9.4 g/dL (80-94g/L)	<8.0 g/dL (<80 g/L)
Leukocyte increase (total WBCs a )	10.8-15.0 x 10  /L (x10  /μL)	>15.0-20.0 x 10  /L (x10  /μL)	>20.0-25.0 x 10  /L (x10  /μL)	>25.0 x 10  /L (x 10  /μL)
Leukocyte decrease (total WBCs a )	2.5-3.5 x 10  /L (x 10  /μL)	1.5-<2.5 x 10  /L (x10  /μL)	1.0-<1.5 x 10  /L (x10  /μL)	<1.0 x 10  /L (x 10  /μL)
Neutrophil decrease (absolute neutrophil count)	1.5-2.0 x 10  /L (x 10  /μL)	1.0-<1.5 x 10  /L (x10  /μL)	0.5-<1.0 x 10  /L (x10  /μL)	<0.5 x 10  /L (x 10  /μL)
Platelets	125-140 x 10  /L (x10  /μL)	100-124 x 10  /L (x10  /μL)	25-99 x 10  /L (x 10  /μL)	<25 x 10  /L (x 10  /μL)
Eosinophils (Absolute)	0.65-1.5 x 10  /L (x 10  /μL)	>1.5-5.0 x 10  /L (x 10  /μL)	>5.0 x 10  /L (x 10  /μL)	Hypereosinophilic
Alanine aminotransferase (ALT b )	1.1-2.5 x ULN c	2.6-5.0 x ULN c	5.1-10.0 x ULN c	>10 x ULN c
Aspartate aminotransferase (AST d )	1.1-2.5 x ULN c	2.6-5.0 x ULN c	5.1-10.0 x ULN c	>10 x ULN c
Alkaline phosphatase	1.1-2.0 x ULN c	2.1-3.0 x ULN c	3.1-10 x ULN c	>10 x ULN c
Total bilirubin (in presence of ALT b or AST d abnormality)	1.1-1.25 x ULN c	1.26-1.5 x ULN c	1.51-1.75 x ULN c	> 1.75 x ULN c
Total bilirubin (in presence of normal ALT b and AST d )	1.1-1.5 x ULN c	1.6-2.0 x ULN c	2.0-3.0 x ULN c	> 3.0 x ULN c

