## 6. ANALYSES AND SUMMARIES

### 6.1. Primary Endpoint(s)

#### 6.1.1. Proportion of Sentinel-Cohort Subjects With Clinical Laboratory Abnormalities Following IP Administration at the 1 Week Follow-Up Visit

##### 6.1.1.1. Primary Analysis

**Endpoint:** Abnormalities in safety laboratory parameters as measured by FDA Grade.

- Analysis timepoints: Visit 2 (1 week after vaccination).
- Analysis population: Safety population.
- Analysis methodology: Descriptive summary statistics.
- Supporting objective: Primary safety objective.

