#### Reporting results:

- Raw data: n and proportion will be presented for each FDA grade (1 thru 4) and laboratory parameters (Hemoglobin, Hematocrit ...) by vaccine group for sentinel cohort subjects only.

**Figures:** None

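### SAP Table 8 gives two grades to total bilirubin at exactly 2.0 x ULN when ALT and AST are normal and, unless ratios are rounded, no grade between adjacent xULN bands

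*SAP*

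**What the plan says.** SAP 6.1.1.1 defines the laboratory endpoint as "Abnormalities in safety laboratory parameters as measured by FDA Grade" at Visit 2 in the sentinel cohorts. Under its reporting results, "n and proportion will be presented for each FDA grade (1 thru 4) and laboratory parameters", by vaccine group.

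The grades come from SAP Table 8 (Section 3.6.3). ALT, AST, alkaline phosphatase and total bilirubin are banded as multiples of the upper limit of normal. Bilirubin has two alternative rows. The stricter one is headed "Total bilirubin (in presence of ALT b or AST d abnormality" and its Grade 3 band is "1.51-1.75 x ULN". The other applies when ALT and AST are both normal, and its Grade 2 and Grade 3 cells are "1.6-2.0 x ULN c 2.0-3.0 x ULN c".

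Other rows of the table are written so that neighbouring bands meet. Leukocyte increase, for instance, has a Grade 2 band starting ">15.0-20.0 x 10". The neutrophil and eosinophil rows also use strict inequalities.

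Section 2 of the SAP says that programming rules are kept in a separate document. That document was not supplied.

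**The concern.** An endpoint counted grade by grade needs each result to map to exactly one grade. A bilirubin of 2.0 x ULN could be tabulated as moderate, as severe, or in both lines. A ratio between two bands has no line at all and could drop out of the by-grade table although it is clearly above normal. These are the liver tests in a first-in-human study. Sentinel subjects must have screening results within the normal range (Protocol 4.2, criterion 5), so any graded Visit 2 result is new.

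**Working it through.** The plan states no figure to reproduce here, so the check is to apply the bands literally. A band a-b is taken as inclusive at both ends and > as strict. Every ratio from just above 1.0 to 12 x ULN was graded at three, two and one decimal places.

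**Inputs (SAP Table 8, multiples of ULN)**

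| Row | Grade 1 | Grade 2 | Grade 3 | Grade 4 |
|---|---|---|---|---|
| ALT, AST | 1.1-2.5 | 2.6-5.0 | 5.1-10.0 | >10 |
| Alkaline phosphatase | 1.1-2.0 | 2.1-3.0 | 3.1-10 | >10 |
| Bilirubin, ALT or AST abnormal | 1.1-1.25 | 1.26-1.5 | 1.51-1.75 | >1.75 |
| Bilirubin, ALT and AST normal | 1.1-1.5 | 1.6-2.0 | 2.0-3.0 | >3.0 |

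**Overlap.** There is exactly one: bilirubin = 2.0 x ULN in the last row, which is Grade 2 and Grade 3. The other three rows have none.

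**Holes between bands, unrounded ratio (open intervals)**

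- ALT and AST: 2.5-2.6 and 5.0-5.1
- Alkaline phosphatase: 2.0-2.1 and 3.0-3.1
- Bilirubin, ALT and AST normal: 1.5-1.6
- Bilirubin, ALT or AST abnormal: 1.25-1.26 and 1.50-1.51

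**Effect of rounding**

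- *One decimal.* No holes remain between bands. The overlap is still there and now covers raw ratios of about 1.95 to 2.05. The stricter bilirubin row, printed to two decimals, is altered: 1.52 rounds to 1.5 and becomes Grade 2, although its printed band is Grade 3.
- *Two decimals.* The stricter bilirubin row is closed. The 0.1-wide holes in the other rows stay open, and 2.00 still has two grades.

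No single precision suits every row, and no precision removes the overlap.

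**Illustration in reported units.** The documents give no ULNs, so these are assumptions.

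- ALT ULN 40 U/L: 2.5 x 40 = 100 and 2.6 x 40 = 104, so 101-103 have no grade. Likewise 5.0 x 40 = 200 and 5.1 x 40 = 204, so 201-203 have none.
- Over ALT ULN 30 to 55 U/L, the lower hole runs from 76-77 (2.5 x 30 = 75, 2.6 x 30 = 78) to 138-142 (2.5 x 55 = 137.5, 2.6 x 55 = 143).
- Bilirubin ULN 1.2 mg/dL: 1.9/1.2 = 1.58, no grade; 2.4/1.2 = 2.0, two grades.
- In 0.1 mg/dL steps, ULNs of 1.0, 1.1, 1.2 and 1.3 all give a double grade at 2.0 x ULN. ULNs of 1.1, 1.2 and 1.3 also give an ungraded value in the 1.5-1.6 hole; 1.0 does not.

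**Weight of one subject.** Protocol Table 1 gives 40 sentinel subjects at each of 3 dose levels, 3 x 40 = 120. One subject is 1/40 = 2.5 percentage points of a cohort. Arm sizes are redacted; if a GBS6 sentinel arm has 10 to 20 subjects, one is 1/20 = 5 to 1/10 = 10 points.

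**The case against.** The best defence is that the bands are meant to be read at printed precision. Hemoglobin (12.4/12.5 g/dL), platelets (124/125), BUN (26/27) and creatinine (1.7/1.8) follow that convention, so the contrast with the white-cell rows may be mixed notation only. A rounding rule may sit in the unsupplied programming rules, and the protocol's text on grading in Section 7.5.3 is partly redacted. This stands as far as the holes go: they exist only if ratios are left unrounded. It does not reach the overlap. It also leaves open which precision applies to a calculated ratio when the rows are printed to different numbers of decimals.

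It is also fair that a bilirubin of 2.0 x ULN is abnormal under either grade. The overlap therefore changes only the split by grade, not whether an abnormality is counted. Laboratory data will be listed as well (SAP 6.7.3), so an ungraded value stays visible.

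Three stronger inferences are tempting and not supported.

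- *That the xULN bands overlap generally, or that the scale cannot grade the endpoint.* The overlap is one point in one row, and nearly all values receive exactly one grade.
- *That slightly raised ALT or AST makes the same bilirubin Grade 2 or Grade 4 at will.* The two rows do differ: 1.8 x ULN is Grade 2 in one and Grade 4 in the other. That is how the two-row scale is designed. Read plainly, an ALT of 1.05 x ULN is not normal, so the stricter row applies. The protocol uses the term in the same sense, relative to the reference range, in the eligibility criteria and in Section 8.4.2.
- *That boundary cases would be settled after the data are seen.* Nothing in the documents says so.

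**Conclusion.** The point holds as a minor defect of the written rule. The overlap at 2.0 x ULN is certain from the table. The holes are conditional on ratios not being rounded, which the supplied text leaves open. The consequence is small: only boundary values are touched, the 120 sentinel subjects were normal at screening, there is one scheduled post-dose draw, and the analysis is descriptive with no decision rules (SAP 5.1). Few if any subjects would change grade. If one did, the shift would be 2.5 points of a sentinel cohort, or 5 to 10 points of an arm under the assumed arm sizes. The protocol's criteria for potential drug-induced liver injury (Section 8.4.2) have their own thresholds and do not depend on Table 8.

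**What to change.** Rewrite the xULN rows as contiguous, non-overlapping bands on the unrounded ratio, with upper limits inclusive as in the leukocyte-increase row. For example:

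- ALT and AST: 1.1 to 2.5, >2.5 to 5.0, >5.0 to 10.0, >10
- Alkaline phosphatase: 1.1 to 2.0, >2.0 to 3.0, >3.0 to 10, >10
- Bilirubin, ALT and AST normal: 1.1 to 1.5, >1.5 to 2.0, >2.0 to 3.0, >3.0
- Bilirubin, ALT or AST abnormal: 1.1 to 1.25, >1.25 to 1.5, >1.5 to 1.75, >1.75

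Add one sentence confirming that the bilirubin row for normal ALT and AST applies only when both are within the reference range. Abnormality should not be defined as 1.1 x ULN or more: that would treat above-normal ALT or AST as normal and lower some bilirubin grades. If redacted protocol text uses the same bands, the two should be reconciled.

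The cost is SAP wording and a few lines of programming, with no new data. A value in a former hole takes the higher adjacent grade, and on the example bands exactly 2.0 becomes Grade 2, a convention for the sponsor to confirm. The bands would depart slightly from the source scale, which the SAP already describes as adapted. Ratios above 1.0 and below 1.1 x ULN remain ungraded, because that is where the scale starts.

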**Table 8. Hematology and Blood Chemistry Toxicity Grading Scale**

	Mild (Grade 1)	Moderate (Grade 2)	Severe (Grade 3)	Grade 4
Blood urea nitrogen (BUN)	23-26 mg/dL	27 – 31 mg/dL	> 31 mg/dL	Requires dialysis
Creatinine	1.5-1.7 mg/dL	1.8-2.0 mg/dL	2.1-2.5 mg/dL	>2.5 mg/dL or requires dialysis

- a. WBC = white blood cell
- b. ALT = alanine aminotransferase
- c. ULN = upper limit of normal
- d. AST = aspartate aminotransferase

### 3.6.4. Physical Examinations, Including Vital Signs

Physical examination will be performed at screening visit (Visit 0) for sentinel subjects and prior to vaccination on Day 1 (Visit 1) for expanded cohort subjects. All physical exam results will be recorded as normal, abnormal or not done in the CRF.

Vital signs including weight, height, sitting systolic and diastolic blood pressure, pulse rate, respiratory rate and oral temperature will be measured at screening visit (Visit 0) for sentinel subjects only and prior to vaccination on Day 1 (Visit 1) for all subjects and recorded in the CRF.

## 3.7. Study Conduct

### 3.7.1. E-diary Completion

On a specific day, the subject is expected to complete all the questions [the 3 local reactions, the 7 systemic events (including fever), and the use of antipyretic medication] in e-diary. In that case, e-diary will be transmitted and considered as complete. The data could be missing in the e-diary for a specific day, in which case it will not be transmitted and considered incomplete. All the data reported on the e-diary will be transferred electronically to the e-diary vendor.

### 3.7.2. Nonstudy Vaccines and Concomitant Treatments

Any nonstudy vaccinations given from the signing of the informed consent to Visit 6 (Month 6) will be recorded in the CRF.

Any medications taken from the signing of the informed consent through Visit 4 (1 month after vaccination) will be recorded in the CRF. Additionally, any medication taken to treat AEs from the signing of the informed consent through Visit 6 (Month 6) will be recorded in the CRF.

Nonstudy vaccines and concomitant medications will be categorized according to the latest version (at time of reporting) of the World Health Organization (WHO) Drug Dictionary.

## 4. ANALYSIS SETS

Data for all subjects will be assessed to determine if subjects meet the criteria for inclusion in each analysis population prior to unblinding and releasing the database and classifications will be documented per standard operating procedures.

### 4.1. Per Protocol Analysis Set

In this study, the per protocol analysis set will be referred to as the evaluable immunogenicity population. The evaluable immunogenicity population will be the primary population for all immunogenicity data analyses. The immunogenicity results will be summarized according to the vaccine group as administered, which by the population definition, is equivalent to the vaccine group as randomized.

The evaluable immunogenicity population will include subjects who:

- Are eligible (have signed informed consent and met all inclusion/exclusion criteria) and randomized into the study;
- Have received GBS6 or placebo as randomized;
- Have a Visit 4 (1 month after vaccination) blood drawn for assay testing within 27 to 45 days, inclusive, after vaccine administration;
- Have at least one valid and determinate assay result for the 1 month after vaccination visit;
- Has no major protocol violation as determined by the study clinician.

Major protocol violations will be determined by clinical review. A major protocol violation is a protocol violation that, in the opinion of the sponsor's global medical monitor would materially affect assessment of immunogenicity, e.g., subject receipt of a prohibited vaccine or medication that might affect immune response or a medication error with suspected decrease in potency of the vaccine. The sponsor's global medical monitor will identify those subjects with protocol violations before any immunogenicity analysis is carried out.

### 4.2. Full Analysis Set

In this study, the full analysis set will be referred to as modified intent-to-treat (mITT) population.

All randomized subjects who have at least one valid and determinate assay result will be included in the mITT population. The immunogenicity results based on mITT population will be summarized according to the vaccine group as randomized and be performed for key immunogenicity endpoint(s). For non-key endpoints, immunogenicity analyses based on the mITT population will be performed only if there is a sizable difference (e.g. ~ 10%) in the

number of subjects between the mITT and the evaluable immunogenicity populations. The key and non-key endpoints are listed below in Table 9.

**Table 9. Analysis Populations for Key and Non-Key Endpoints**

Endpoint	Analysis Based on Evaluable Immunogenicity Population	Analysis Based on mITT Population
Key Immunogenicity Endpoint		
GBS serotype-specific IgG GMCs measured 1 month after vaccination	Yes	Yes
Non Key Immunogenicity Endpoint(s)		
CCI		

### 4.3. Safety Analysis Set

In this study, the safety analysis set will be referred to as the safety population.

All subjects who received GBS6 vaccine or placebo injection will be included in the safety population. For the safety analyses, subjects will be analyzed according to the vaccine group as administered. The safety population is the analysis population for all the safety endpoints.

### 4.4. Other Analysis Sets

No other analysis sets will be defined in this study.

### 4.5. Treatment Misallocations

- Randomized but not vaccinated: these subjects will not be included in the safety population for safety analyses. These subjects will not be included in the evaluable

immunogenicity population, but they will be included in the mITT population for immunogenicity analyses for subjects with valid and determinant assay results. The immunogenicity results for these subjects will be reported under the vaccine group as randomized.

- Vaccinated but not randomized: these subjects will be included in the safety population for safety analyses and will be reported under the vaccine group based on the vaccine received. They will be excluded from immunogenicity analyses based on either evaluable immunogenicity or mITT populations.
- Randomized but received incorrect vaccine: these subjects will be included in the mITT population for immunogenicity analyses if any assay results are available and will be reported under the vaccine group based on the randomized vaccine group in the analysis. These subjects will also be included in the safety population for safety analysis and will be reported under the vaccine group based on the vaccine received. These subjects will be excluded from the evaluable immunogenicity population for immunogenicity analyses.

